2.3 Exploratory (Correlative) Objectives

1. To define the immunologic infiltration within bladder tissue following administration of neoadjuvant combination treatment with atezolizumab and tiragolumab when compared to pre-treatment TURBT biopsies
2. To assess the immunologic impact of combined tiragolumab and atezolizumab regimen in the urothelial cancer tumor microenvironment (Cohort B) in comparison to the impact on the tumor microenvironment of atezolizumab monotherapy in a similar cohort of patients treated with neoadjuvant atezolizumab for MIBC at UCSF (Cohort A)
3. To assess for tumor-based biomarkers of response and resistance to this combination therapy using single-cell RNA sequencing (scRNA-seq) and high-dimensional flow cytometry
4. To define the treatment-induced effects on circulating immune cells with this combination therapy
5. To assess the presence of antigen-specific immune responses to a broad panel of candidate tumor antigens

Endpoints:

- Immunohistochemistry and gene expression analysis for immune cell subset quantification and localization within resected tumors, in particular through the comparison of intratumoral environment of post-treatment cystectomies to pre-treatment TURBTs
- Flow cytometry to evaluate changes in intratumoral and circulating immune cells
- T cell receptor (TCR) deep sequencing of tissue samples from pre-treatment biopsies and post-treatment resected tissues, and post-cystectomy circulating T cells.
- Immune response mRNA expression analysis to derive signatures associated with tumor response
- Identification of genomic mutations and gene copy aberrations associated with response and resistance to therapy
- Antigen array-base detection of circulating antibody responses
- Flow cytometry to evaluate changes in intratumoral and circulating immune cells
- T cell receptor (TCR) deep sequencing of tissue samples from pre-treatment biopsies and post-treatment resected tissues, and post-cystectomy circulating T cells.
- Immune response mRNA expression analysis to derive signatures associated with tumor response (expansion only)

- Identification of genomic mutations and gene copy aberrations associated with response and resistance to therapy (expansion only)
- Antigen array-base detection of circulating antibody responses (expansion only)

3 Study Design

3.1 Characteristics

This is a single arm, open-label multiple-cohort Phase II study of atezolizumab-based neoadjuvant therapy in subjects with muscle-invasive bladder cancer appropriate for cystectomy and refusing or ineligible for neoadjuvant cisplatin-based chemotherapy. This study has two cohorts (Cohort A and Cohort B) and will accrue each cohort sequentially (i.e., Cohort A will fully accrue, then Cohort B). Cohort A participants will receive neoadjuvant atezolizumab monotherapy and Cohort B participants will receive combination neoadjuvant treatment with atezolizumab and tiragolumab. As of October 2020, Cohort A has finished dose escalation and is in dose-expansion.

Following the administration of all intended neoadjuvant treatment regimen, participants will undergo cystectomy to evaluate pathologic response to treatment and for immunologic characterization in the resected tissue. Surgery should be performed within 12 weeks from the start of neoadjuvant treatment. Any treatment-related delays that put the surgery outside of this window will be considered an adverse event.

Serum and urine will be obtained as well to characterize circulating immune responses. Patients will be followed clinically for up to 2 years to assess for disease recurrence.

While adjuvant Atezolizumab was initially offered to patients in Cohort A who had pT3/pT4 or pN+ disease, given the lack of efficacy of adjuvant atezolizumab observed in the IMvigor 010 trial, no further adjuvant therapy will be offered to patients.

Cohort A (Atezolizumab monotherapy)

[figure not shown]
- Multi-dose phase (fully accrued): Enrolled patients will be assigned sequentially to atezolizumab dose levels in cohorts of 6 patients per dose level. The starting dose level is 1200mg x 1 dose and will be escalated in subsequent cohorts to 1200mg q 3 weeks x 2 doses, and finally 1200mg q 3 weeks x 3 doses.
- Expansion phase: After completion of the multi-dose phase, Cohort A expansion will open and up to 27 enrolled participants will receive atezolizumab 1200mg q 3 weeks x 3 doses prior to cystectomy.

Cohort B (Atezolizumab + tiragolumab)

After completion of Cohort A, Cohort B will open and enrolled patients will receive atezolizumab (1200mg IV on Day 1 of a 21 day cycle) and tiragolumab (600mg IV on Day 1 of a 21 day cycle) as neoadjuvant treatment for an intended total of three treatment cycles prior to an intended radical cystectomy.

- Safety Lead-in (see schema below):
 - **Dose Level 1** (Atezolizumab 1200 mg x 3 cycles, Tiragolumab 600 mg x 3 cycles): There will be an initial safety lead in of 6 patients treated with this regimen, at which time enrollment will pause to assess the safety of this combination treatment. As long as no more than 1 out of the initial 6 patients experience dose limiting toxicities (DLTs) or a delay in the time to radical cystectomy, the remaining patients will enroll at the same dose and regimen.
 - If two or more patients out of the initial six experience DLTs within the first cycle (3 weeks), accrual will be halted and the combination reevaluated.
 - If two or more patients out of the initial six experience DLTs within the first 2 cycles (6 weeks), accrual to this dose level will be halted and we will move to dose level 3.
 - If two or more patients out of the initial six experience DLTs or delay in the time to radical cystectomy, and no more than 1 patient experienced DLTs during the first 2 cycles (6 weeks), the next six patients will be treated at dose level 2
 - **Dose Level 2** (Atezolizumab 1200 mg x 3 cycles, Tiragolumab 600 mg x 2 cycles): As long as no more than 1 out of 6 patients experience DLTs or a delay in the time to radical cystectomy with this treatment, the remaining patients will enroll at the same dose and regimen.
 - If two or more patients out of the six patients experience DLTs within the first cycle (3 weeks), accrual will be halted and the combination reevaluated.
 - If two or more patients out of the six experience DLTs or delay in the time to radical cystectomy, and no more than 1 patient experienced DLTs during the first cycle (3 weeks), the next six patients will be treated at dose level 3
 - **Dose Level 3** (Atezolizumab 1200 mg x 3 cycles, Tiragolumab 600 mg x 1 cycle): This will be the selected regimen if no more than 1 out of 6 patients experience DLTs or a delay in the time to radical cystectomy. However if 2 or more patients experience DLTs or a delay in the time to radical cystectomy with this combination regimen, then accrual will be halted and the combination reevaluated.
- Expansion: Once the intended treatment regimen is established following completion of the safety assessment, an additional 15 patients will be enrolled at the same regimen for a total of 21 patients on that treatment regimen.

Cohort B Safety Lead-in Schema

3.2 Number of Participants

Total Cohort A accrual: Up to 27 participants

- Cohort A Safety Lead-In: 18 participants (already accrued as of October 2020)
- Cohort A Expansion: Up to 9 additional participants may be accrued so that Cohort A expansion group = up to 15 total participants treated at established regimen (6 participants treated at highest administered dose from multi-dose portion + up to 9 additional participants).

Total Cohort B accrual: 21-33 patients

- Cohort B Safety Lead-In: 6-18 patients will be included.
- Cohort B Expansion: 15 additional patients treated with the regimen established during the safety lead-in phase (21 total treated with established regimen)

3.3 Eligibility Criteria

Patients must have baseline evaluations performed prior to the first dose of study drug and must meet all inclusion and exclusion criteria. In addition, the patient must be thoroughly informed about all aspects of the study, including the study visit schedule and required evaluations and all regulatory requirements for informed consent. The written informed consent must be obtained from the patient prior to enrollment. The following criteria apply to all patients enrolled onto the study unless otherwise specified.

3.3.1 Inclusion Criteria

In order to be eligible to participate in this study, an individual must meet all of the following criteria:

1. 18 years of age or older
2. ECOG performance status 0-1
3. Histologically documented transitional cell carcinoma with the presence of any of the following stages: grade cT2-T4a, considered appropriate for radical cystectomy. Subjects with mixed histology are required to have a dominant TCC pattern.
4. Patients not suitable for neoadjuvant cisplatin-based chemotherapy as determined by the following:
 - a. Creatinine clearance less than 60ml/min. GFR should be assessed by calculation from serum/plasma creatinine (Cockcroft-Gault formula)
 - b. CTCAE Gr \geq 2 hearing loss
 - c. CTCAE Gr \geq 2 neuropathy
5. Subjects with MIBC not meeting the above criteria are still eligible provided the patient declines neoadjuvant cisplatin-based chemotherapy, after specific informed consent describing the known benefits of cisplatin-based chemotherapy. The reason for declining must be documented.
6. Adequate bone marrow function defined as:
 - a. WBC $>$ 2500 cells/mm³
 - b. ANC $>$ 1500 cells/mm³
 - c. Hemoglobin $>$ 9 g/dL. Patients may be transfused or receive erythropoietic treatment to meet this criterion.
 - d. Platelet count $>$ 100,000 cells/mm³
7. Adequate renal function: Calculated CrCl $>$ 30ml/min
8. Serum bilirubin $<$ 1.5 x ULN (except for patients with documented Gilbert's disease)

9. AST and ALT < 2.5 x ULN
10. Ability to understand and willingness to sign a written informed consent.
11. Have available evaluable archival tumor tissue for PD-L1 biomarker assessment. Presence of PD-L1 antigen on tumors is NOT required for study entry.
12. The effects of atezolizumab or tiragolumab on the developing human fetus are unknown. For this reason women of child-bearing potential and men must agree to use adequate contraception prior to study entry, during study participation, and for 5 months after study treatment discontinuation. Should a woman become pregnant or suspect she is pregnant while she or her partner is participating in this study, she should inform her treating physician immediately. Men treated or enrolled on this protocol must also agree to use adequate contraception prior to the study, for the duration of study participation, and for 90 days after completion of study drug administration.

3.3.2 Exclusion Criteria

Individuals who meet any of the following criteria are not eligible to participate in this study:

1. Subjects with primary TCC of the ureter, urethra, or renal pelvis without TCC of the bladder are not allowed.
2. Known distant metastatic disease (e.g. pulmonary or hepatic metastases).
 - a. Subjects with malignant lymphadenopathy in the abdomen or pelvis considered appropriate for radical cystectomy and lymphadenectomy with the goal of complete resection of all malignant disease are allowed.
3. Intravesical chemo- or biologic therapy within 6 weeks of first treatment.
4. Prior systemic chemotherapy, immunotherapy or radiation therapy for transitional cell carcinoma of the bladder.
 - a. Subjects who have received prior intravesical chemotherapy or intravesical immunotherapy (e.g., interferon) are allowed.
5. Prior treatment with, anti-TIGIT antibodies, CD137 agonists or immune checkpoint blockade therapies, including anti CTLA-4, anti-PD1 and anti-PD-L1 therapeutic antibodies.
6. History of autoimmune disease, including but not limited to myasthenia gravis, myositis, autoimmune hepatitis, systemic lupus erythematosus, rheumatoid arthritis, inflammatory bowel disease, vascular thrombosis associated with antiphospholipid syndrome, Wegener's granulomatosis, Sjogren's syndrome, Guillain-Barre syndrome, multiple sclerosis, vacuities, or glomerulonephritis.
 - a. Patients with a history of autoimmune-related hypothyroidism on a stable dose of thyroid replacement hormone are eligible for this study.
 - b. Patients with controlled Type I diabetes mellitus on a stable dose of insulin regimen are eligible for this study.

7. History of idiopathic pulmonary fibrosis, organizing pneumonia (e.g., bronchiolitis obliterans), drug-induced pneumonitis, idiopathic pneumonitis, or evidence of active pneumonitis on screening chest CT scan.
 - a. History of radiation pneumonitis in the radiation field (fibrosis) is permitted.
8. HIV or active hepatitis B (HBV; chronic or acute; defined below) or active hepatitis C
 - a. Patients with resolved HBV infection (defined as the presence of hepatitis B core antibody [HBc Ab] and absence of HBsAg) are eligible. HBV DNA must be obtained in these patients prior to Cycle 1, Day 1, but detection of HBV DNA in these patients will not exclude study participation.
 - b. Patients positive for hepatitis C virus (HCV) antibody are eligible only if polymerase chain reaction is negative for HCV RNA.
9. Active tuberculosis
10. Positive Epstein-Barr virus (EBV) viral capsid antigen IgM test at screening
 - a. An EBV polymerase chain reaction (PCR) test should be performed as clinically indicated to screen for acute infection or suspected chronic active infection. Patients with a positive EBV PCR test are excluded.
11. Severe infections within 4 weeks prior to Cycle 1, Day 1, including but not limited to hospitalization for complications of infection, bacteremia, or severe pneumonia
12. Prior allogeneic stem cell or solid organ transplant
13. Administration of a live, attenuated vaccine within 4 weeks before Cycle 1, Day 1 or anticipation that such a live attenuated vaccine will be required during the study. Inactivated vaccines (such as hepatitis A or polio vaccines) are permitted during the study.
 - a. Influenza vaccination should be given during influenza season only (approximately September to March). Patients must not receive live attenuated influenza vaccine (e.g., FluMist) within 4 weeks prior to Cycle 1, Day 1 and for at least 12 weeks after the last dose.
14. Clinically significant active infection or uncontrolled medical condition based on the discretion of the treating physician
15. Uncontrolled cystitis, significant bladder pain or spasms, or gross hematuria that in the opinion of the treating investigator, should preclude study entry.
16. Significant cardiovascular disease, such as New York Heart Association cardiac disease (Class II or greater), myocardial infarction within the previous 3 months, unstable arrhythmias, or unstable angina
 - a. Patients with known coronary artery disease, congestive heart failure not meeting the above criteria, or left ventricular ejection fraction < 50% must be on a stable medical regimen that is optimized in the opinion of the treating physician, in consultation with a cardiologist if appropriate.

17. Major surgical procedure other than for diagnosis within 28 days prior to Cycle 1, Day 1 or anticipation of need for a major surgical procedure other than cystectomy during the course of the study
18. Treatment with systemic corticosteroids or other systemic immunosuppressive medications (including but not limited to prednisone, dexamethasone, cyclophosphamide, azathioprine, methotrexate, thalidomide, and anti-tumor necrosis factor [anti-TNF] agents) within 2 weeks prior to Cycle 1, Day 1, or anticipated requirement for systemic immunosuppressive medications during the trial
 - a. Patients who have received acute, low-dose, systemic immunosuppressant medications (e.g., a one-time dose of dexamethasone for nausea) may be enrolled in the study after discussion with and approval by the Study Chair.
 - b. The use of inhaled corticosteroids and mineralocorticoids (e.g., fludrocortisone for adrenal insufficiency) is allowed.
19. Pregnant or nursing women are excluded
20. Known hypersensitivity to Chinese hamster ovary (CHO) cell products or any component of the atezolizumab or tiragolumab formulation
21. History of severe allergic, anaphylactic, or other hypersensitivity reactions to chimeric or humanized antibodies or fusion proteins
22. Malignancies other than UC within 3 years prior to Cycle 1, Day 1, with the exception of those with a low risk of metastasis or death treated with expected curative outcome (such as, but not limited to, adequately treated carcinoma in situ of the cervix, basal or squamous cell skin cancer, localized prostate cancer treated with curative intent and absence of PSA relapse, or ductal carcinoma in situ of the breast treated surgically with curative intent) or incidental prostate cancer (T1a, Gleason score ≤ 6 and PSA < 0.5 ng/mL).

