1.4 Background on Atezolizumab

Atezolizumab is a human immunoglobulin (IgG1) monoclonal antibody that is produced in Chinese hamster ovary (CHO) cells. It targets programmed death-ligand 1 (PD-L1) on antigen-presenting cells or tumor cells and prevents interaction with programmed death-1 (PD-1) receptor, which is an inhibitory receptor expressed on T cells. Atezolizumab also blocks the interaction between PD-L1 and B7.1. Interference of the PD-L1:PD-1 and PD-L1:B7.1 interactions may enhance the magnitude and quality of the tumor-specific T-cell response through increased T-cell priming, expansion, and/or effector function.

Atezolizumab was engineered to eliminate Fc-effector function via a single amino acid substitution at position 298 on the heavy chain, which results in a non-glycosylated antibody that has minimal binding to Fc receptors and, consequently, eliminates detectable Fc-effector function.

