1.6 Background and Clinical Studies of Tiragolumab

Tiragolumab is a fully human immunoglobulin G1 (IgG1)/kappa mAb derived in Open Monoclonal Technology (OMT) rats that binds T-cell Immunoreceptor with Immunoglobulin and Immunoreceptor Tyrosine-Based Inhibition Motif [ITIM] domains (TIGIT) and prevents its interaction with the poliovirus receptor (PVR). The recombinant antibody is produced in Chinese hamster ovary (CHO) cells and consists of two heavy chains (456 amino acid residues each) and two light chains (220 amino acid residues each).

The inhibitory immunoreceptor TIGIT has been shown to limit the effector function of tumor-associated lymphocytes. TIGIT is an immunoglobulin (Ig) super family member expressed on subsets of activated T cells and natural killer (NK) cells, and found highly expressed in tumor tissue and in tumor-infiltrating immune cells in many human cancers, including, but not limited to NSCLC, breast cancer, multiple myeloma, and non-Hodgkin lymphoma. In multiple tumor types, TIGIT is coordinately expressed with PD-1²¹⁻²³. Genetic ablation or antibody blockade of TIGIT has been shown to enhance NK cell killing, CD4+ and CD8+ T-cell activation, and effector function in vitro and in vivo in nonclinical models.^{21, 22, 24, 25} In the nonclinical tumor models, TIGIT interacted with high affinity to CD155 (also known as PVR), which also has an activating counter-receptor CD226. Activation of TIGIT on T cells and NK cells was demonstrated to limit proliferation, effector cytokine production, and killing of target tumor cells.^{21, 22, 24}

Therapeutic blockade of TIGIT by tiragolumab represents an attractive strategy for cancer therapy and is expected to enhance the magnitude and quality of the tumor-specific T-cell responses, which may result in improved meaningful anti-tumor activity when tiragolumab is used in combination with other cancer immunotherapies and administered with chemotherapy. The available nonclinical and clinical data provide a strong rationale for evaluating the potential clinical benefit of tiragolumab in cancer patients. Refer to the tiragolumab Investigator's Brochure for details on nonclinical studies.

Clinically study GO30103²⁶ is a first-in-human, open-label, multicenter, global, dose-escalation/dose-expansion Phase I study designed to evaluate the safety, tolerability, and pharmacokinetics of tiragolumab as a single agent (Phase Ia) and in combination with

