doses ≥ 1 mg/kg, the mean Cmax increased in a dose-proportional manner and was 26.0 $\mu\text{g}/\text{mL}$ for the 1-mg/kg dose group and 486 $\mu\text{g}/\text{mL}$ for the 20-mg/kg dose group. Similarly, at doses ≥ 1 mg/kg, the group mean AUC $0-\infty$ had a range of 340–6050 day \times $\mu\text{g}/\text{mL}$ for 1-mg/kg and 20-mg/kg dose group and was approximately dose proportional, as evidenced by similar CL across the dose range. The observed CL and Vss for Atezolizumab at doses ≥ 1 mg/kg are consistent with these of a typical IgG1 antibody in humans. The development of anti-therapeutic antibodies (ATAs) has been observed in patients in all dose cohorts and was associated with changes in pharmacokinetics for some patients in the lower dose cohorts (0.3, 1, and 3 mg/kg). Patients dosed at the 10-, 15-, and 20-mg/kg dose levels have maintained the expected target trough levels of drug despite the detection of ATAs. Accordingly, the development of detectable ATAs does not appear to have a clinically significant impact on pharmacokinetics for doses from 10 to 20 mg/kg. To date, no relationship between the development of measurable ATAs and safety or efficacy has been observed.

The expected metabolic products of proteins and peptides, including IgG1 monoclonal antibodies such as atezolizumab, are small peptides and individual amino acids. Cytochrome P450 enzymes as well as conjugation/glucuronidation reactions are not involved in the metabolism of Atezolizumab.

Contraindications

Atezolizumab is contraindicated for patients with the following:

- History of severe allergic anaphylactic reactions to chimeric, human or humanized antibodies, or fusion proteins
- Known hypersensitivity to CHO cell products or any component of the atezolizumab formulation.

As with all investigational products, unknown side effects may occur. Patients should be monitored closely throughout their participation in clinical studies of Atezolizumab.

Availability

The atezolizumab drug product is provided in a single-use, 20-mL USP/Ph. Eur. Type 1 glass vial as a colorless to slightly yellow, sterile, preservative-free clear liquid solution intended for IV administration. The vial is designed to deliver 20 mL (1200 mg) of Atezolizumab solution but may contain more than the stated volume to enable delivery of the entire 20 mL volume. The Atezolizumab drug product is formulated as 60 mg/mL atezolizumab in 20 mM histidine acetate, 120 mM sucrose, 0.04% polysorbate 20, pH 5.8.

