4.1.2 Tiragolumab

Classification

Tiragolumab is a fully human IgG1 monoclonal antibody. The recombinant antibody is produced in CHO cells, and consists of two heavy chains (456 amino acid residues each) and two light chains (220 amino acid residues each). There are two N-linked glycosylation sites (Asn306) in the Fc domain.

Mechanism of Action

Tiragolumab binds to TIGIT and prevents its interaction with Poliovirus receptor (PVR). The inhibitory immunoreceptor TIGIT has been shown to limit the effector function of tumor-associated lymphocytes.

Pharmacokinetics and Metabolism

Preliminary population-PK analyses show that tiragolumab exposures increased approximately dose-proportionally following IV administration at doses ranging from 100 to 1200 mg Q3W as monotherapy or in combination with 1200 mg Q3W atezolizumab. Preliminary population-PK analysis estimated tiragolumab clearance at 0.28 L/day with a linear drug elimination half-life of approximately 15 days.

Contraindications

Tiragolumab is contraindicated for patients with a history of severe allergic anaphylactic reactions to chimeric, human, humanized antibodies, or fusion proteins because of the potential for severe reactions.

Availability

The tiragolumab drug product will be supplied in single-use, 15-mL glass vials. The vials contain 10 mL of tiragolumab drug product and are buffered in histidine solution containing polysorbate 20, sucrose, L-methionine, and WFI. The approximate concentration of tiragolumab antibody in the vials is 60 mg/mL.

Storage and handling

The recommended storage condition for the tiragolumab drug product is 2°C-8°C (36°F–46°F). Do not shake or freeze IV bags containing dose solution. Protect from direct sunlight (exposure to indoor ambient light is acceptable).

Tiragolumab must be prepared for dosing under appropriate aseptic conditions as it does not contain antimicrobial preservatives. The dose solution should be used immediately. If not used immediately, the total storage time of the dose solution prior to administration should not exceed 24 hours to limit the risk of microbial growth in case of accidental contamination.

Side Effects

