For the first infusion, the patient's vital signs (heart rate, respiratory rate, blood pressure, and temperature) should be determined within 60 minutes before, during (every 15 [\pm 5] minutes), and 30 (\pm 10) minutes after the infusion. For subsequent infusions, vital signs will be collected within 60 minutes before infusion, and during or after the infusion if clinically indicated or if symptoms occurred in the prior infusion. Patients will be informed about the possibility of delayed post-infusion symptoms and instructed to contact their study physician if they develop such symptoms.

No premedication will be allowed for the first dose of atezolizumab. Premedication may be administered for Cycles \geq 2 at the discretion of the treating physician after consultation with the Study Chair.

Tiragolumab dose will be administered following the dose of atezolizumab and will be delivered over 60 (\pm 15) minutes. If the first infusion is tolerated without infusion-associated adverse events, the second infusion may be delivered over 30 (\pm 10) minutes. If the 30-minute infusion is well tolerated, all subsequent infusions (for subjects receiving more than 2 doses) may be delivered over 30 (\pm 10) minutes.

For the first infusion, the patient's vital signs (heart rate, respiratory rate, blood pressure, and temperature) should be determined within 60 minutes before, during (every 15 [\pm 5] minutes), and 30 (\pm 10) minutes after the infusion. For subsequent infusions, vital signs will be collected within 60 minutes before infusion, and during or after the infusion if clinically indicated or if symptoms occurred in the prior infusion. Patients will be informed about the possibility of delayed post-infusion symptoms and instructed to contact their study physician if they develop such symptoms.

No premedication will be allowed for the first dose of tiragolumab. Premedication may be administered for Cycles ≥ 2 at the discretion of the treating physician after consultation with the Study Chair.

Table 5.1 Regimen Description

Study Drug	Premedication; precautions	Dose	Route	Schedule	Cycle Length
Atezolizumab	None for 1 st dose	1200mg	Intravenous	Day 1 each cycle	21 days
Tiragolumab (Cohort B only)	None for 1 st dose	600mg	Intravenous	Day 1 each cycle	21 days

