5.7 Monitoring and Toxicity Management

5.7.1 Eligibility

Eligibility criteria were selected to guard the safety of patients in this trial. Results from the nonclinical toxicology studies with atezolizumab and tiragolumab, as well as the nonclinical/clinical data from other PD-L1/PD-1 inhibitors, were taken into account. Specifically, patients at risk for study- emergent autoimmune conditions or with a prior diagnosis of autoimmune disease, patients with evidence of acute infections, and patients who have received a live-attenuated viral vaccine within 4 weeks before Day 1 are excluded from the study.

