6.1 Informed Consent Forms and Screening Log

A written, signed, informed consent form (ICF) and a Health Insurance Portability and Accountability Act (HIPAA) authorization must be obtained before any study-specific assessments are initiated. A copy of the signed ICF will be given to the subject and a copy will be filed in the medical record. The original will be kept on file with the study records. Informed

Consent Forms for enrolled patients and for patients who are not subsequently enrolled will be maintained at the study site.

All patients who are consented will be registered in OnCore®, the UCSF Helen Diller Family Comprehensive Cancer Center Clinical Trial Management System (CTMS). The system is password protected and meets HIPAA requirements.

Each participating site is responsible for OnCore® registration of study participants consented at the site.

All screening evaluations must be completed and reviewed to confirm that patients meet all eligibility criteria before enrollment. The investigator will maintain a screening log to record details of all patients screened and to confirm eligibility or record reasons for screening failure, as applicable.

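### Exclusion criterion 21 leaves out human antibodies, so a patient with a stated contraindication to both study drugs can pass the eligibility list

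*Combined protocol and SAP*

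**What the plan says.** Criterion 21 in section 3.3.2 excludes "History of severe allergic, anaphylactic, or other hypersensitivity reactions to chimeric or humanized antibodies or fusion proteins".

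Section 4.1.1 lists as a contraindication to atezolizumab "History of severe allergic anaphylactic reactions to chimeric, human or humanized antibodies, or fusion proteins". Section 4.1.2 states that "Tiragolumab is contraindicated for patients with a history of severe allergic anaphylactic reactions to chimeric, human, humanized antibodies, or fusion proteins", and gives the potential for severe reactions as the reason.

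The protocol places both drugs in the human class: "Atezolizumab is a human immunoglobulin (IgG1) monoclonal antibody" (section 1.4) and "Tiragolumab is a fully human immunoglobulin G1 (IgG1)/kappa mAb" (section 1.6). Sections 4.1.1 and 4.1.2 repeat this under Classification.

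On the purpose of the list, section 5.7.1 says "Eligibility criteria were selected to guard the safety of patients in this trial", and section 6.1 says "All screening evaluations must be completed and reviewed to confirm that patients meet all eligibility criteria before enrollment".

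**The concern.** The eligibility list is what a site works through before enrolling a patient. It should be at least as strict as the contraindications the protocol states for the drugs it gives. Here it is looser on one point, and that point is the antibody class of both study drugs. A site that applied section 3.3.2 exactly as written could enroll someone whom section 4.1 says should receive neither drug.

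If the contraindication were then also missed, the patient would receive first infusions of two human antibodies without premedication: "No premedication will be allowed for the first dose of atezolizumab" (section 5.1, which sets the same rule for tiragolumab). That rule applies to every patient and is not itself a fault, but it means a wrongly enrolled patient has no added protection at the first exposure. If the contraindication were noticed after enrollment, the result would be a late screen failure or a patient who may be replaced before dosing (section 8.3.1).

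**Working it through.** No arithmetic applies. The check is a comparison of texts, followed by a search for anything else that closes the gap.

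**Step 1. Antibody classes named.**

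| Class | Criterion 21 (3.3.2) | Atezolizumab (4.1.1) | Tiragolumab (4.1.2) |
|---|---|---|---|
| Chimeric | yes | yes | yes |
| Human | **no** | yes | yes |
| Humanized | yes | yes | yes |
| Fusion proteins | yes | yes | yes |

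The two contraindications name the same four classes. Criterion 21 names three of them.

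**Step 2. Reaction types named.** Section 4.1 is limited to severe allergic anaphylactic reactions. Criterion 21 adds other hypersensitivity reactions, so it is wider in this respect. The gap concerns antibody class only. The wider reaction wording also suggests that no narrower safety screen was intended, and the protocol gives no reason for admitting these patients.

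**Step 3. Could another criterion catch the patient?** Of the 22 exclusion criteria, these come closest:

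- Criterion 20 requires known hypersensitivity to CHO cell products or to a component of either formulation. It catches a past reaction to a CHO-derived human antibody only if the reaction is recognized as such.
- Criterion 5 removes patients already treated with anti-TIGIT antibodies, CD137 agonists or checkpoint inhibitors, and no others.
- Criterion 4 removes prior systemic immunotherapy for transitional cell carcinoma of the bladder. Criterion 6 removes most autoimmune disease. Criterion 22 removes most other cancers within 3 years. These exclude some settings in which an earlier antibody could have been given, but not all.
- Criterion 14 concerns active infection or an uncontrolled condition. A past reaction is neither.

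No inclusion criterion deals with drug allergy, and no criterion refers to the contraindications in section 4.1.

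**Step 4. Follow one patient through.** Take a patient with past anaphylaxis to a human antibody outside the groups in criterion 5, no known hypersensitivity to CHO products or formulation components, and nothing else that excludes. Under section 3.3 this patient is eligible. Under sections 4.1.1 and 4.1.2 the same patient is contraindicated for both drugs. The two parts of the current protocol give opposite answers.

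**The case against.** The strongest reply is that the protocol already forbids this dosing. The contraindication is stated once for each drug, and section 9.5 binds the site's principal investigator to use the drug only as the protocol specifies. Other provisions also help. A complete medical and prior-treatment history is taken at screening (6.9.1), dosing requires an acceptable clinical assessment (section 6), the investigator may withdraw a patient when continued participation seems imprudent (6.9.7), and treatment must stop for a condition that jeopardizes safety (6.9.8). If a reaction did occur, there are emergency facilities, vital signs every 15 minutes during the first infusion (5.1) and an anaphylaxis procedure (Appendix 5). This stands as far as it goes: several independent safeguards would have to fail before harm occurred, and section 4.1 is not the only one. But these provisions are general, discretionary or applied after the fact. None makes the eligibility rule agree with the contraindication.

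A second reply is that adding *human* while keeping the wider reaction wording goes further than section 4.1, because it would also exclude some patients whose reaction to a human antibody was not anaphylactic. That is true. It would, however, only treat human antibodies as criterion 21 already treats chimeric and humanized ones.

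A third reply is that neither the rarity of such histories nor the low cost of the change has a source in the documents. That is fair: both are judgments and are offered as such.

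**Conclusion.** The concern holds. Criterion 21 omits the antibody class of both study drugs, and a patient contraindicated under sections 4.1.1 and 4.1.2 can satisfy the eligibility list.

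The practical effect is small. It depends on a history that is expected to be rare and on a site failing to act on section 4.1 or on the general safety provisions. The documents give no frequency for such a history, nor for a reaction after it, so no count of affected patients is offered and no effect on the number of dose-limiting toxicities is claimed. The 21 to 33 patients planned for Cohort B are those to whom the criterion applies, not an estimate of those at risk. Endpoints, power and analysis are untouched.

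It should still be corrected, because it is a definite inconsistency in a safety criterion and costs almost nothing to remove.

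**What to change.** At the next amendment, insert *human* into criterion 21 so that its antibody classes are chimeric, human and humanized, followed by fusion proteins as now. Keep its existing wording on reaction type. Sections 4.1.1 and 4.1.2 need no change.

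The cost is one word and, at most, an occasional extra screen failure. Some of those failures may be patients with a non-anaphylactic reaction to a human antibody, whom section 4.1 alone would not bar.
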